### 7.2. Other Efficacy Endpoints

#### 7.2.1. Percent CFB in Lactate Dehydrogenase (LDH)

Descriptive statistics for the observed values, changes from baseline, and percent changes from baseline in LDH in the safety population will be presented for all scheduled visits during the treatment period. Unscheduled visits will be presented in the data listings but not summarized in the table.

## **8. SAFETY AND TOLERABILITY**

All study safety data to support the aCSR will be presented in data listings.

AEs will be assessed and recorded from the time of signing of the informed consent through the appropriate follow-up period. AEs will be mapped to MedDRA version 24.0 preferred term (PT) and system organ class (SOC). Relationship to study treatment will be assessed as not related, unlikely related, possibly related, probably related, or definitely related. AEs will be graded according to the CTCAE scales (Version 5.0, 27 November 2017). AEs not covered by CTCAE criteria will be assessed for severity as mild, moderate, severe, or life-threatening, corresponding to toxicity Grades 1 through 4.

### **8.1. Overall Summary of Treatment-emergent Adverse Events**

The overall summary of TEAEs table for all subjects in the safety population will summarize the number and percentage of subjects that report at least 1 TEAE, have a treatment-related TEAE, have a TEAE leading to treatment withdrawal, have a serious TEAE requiring concomitant medication, have a severe (Grade 3) or life-threatening (Grade 4) TEAE, have a serious TEAE, have a TEAE leading to study discontinuation, and have a TEAE leading to death. In addition to summarizing the number and percentage of subjects that have at least 1 of these events, the table will also summarize the total number and percentage for each of these events. Results will be summarized for the BCX9930 400 mg BID, dose taper and Total. The percentages for number of subjects will use the safety population sample size as the denominator; the percentages for the number of events will use the total number of TEAEs as the denominator.

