Subjects will be eligible to receive study drug (BCX9930) under this version of the protocol for up to 96 weeks for as long as the investigator believes it is in the subject's best interest to continue treatment, or until the subject has access to another therapy for PNH, whichever comes first. Treatment with BCX9930 will be discontinued for subjects who are deriving no meaningful clinical benefit, or who experience an unacceptable drug-related AE or are otherwise intolerant of study drug.

An independent BCX9930 program-wide DMC will provide oversight of the safety of subjects receiving BCX9930 in this study.

*Methodology:*

Subjects who meet all of the inclusion and none of the exclusion criteria can be enrolled into Study 205. The last on-treatment visit completed for the prior study will also serve as the baseline visit for Study 205. If subjects have completed at least 24 weeks of BCX9930 treatment in the prior study, study visits will occur every 8 weeks to Week 48, then every 12 weeks until Week 96. Subjects who have not completed 24 weeks of treatment with BCX9930 prior to enrolling in Study 205 must return to the clinic every 4 weeks until they have completed 24 weeks of cumulative treatment with BCX9930. Subjects who discontinue treatment with BCX9930 for any reason (complete study visits or discontinue early), will be asked to complete an end-of-study or early termination visit, as applicable, approximately 3 weeks ( $\pm$  3 days) after the last dose of BCX9930.

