### **3. STUDY DESIGN**

#### **3.1. Summary of Study Design**

This study is designed to provide continued access to BCX9930 for subjects currently receiving treatment with BCX9930 in another BioCryst-sponsored clinical study for PNH (i.e., Studies 201, 202, or 203, hereafter referred to as the “prior study”) who, in the opinion of the investigator, have both benefited from treatment with BCX9930 and would benefit from continued treatment with BCX9930, who wish to continue treatment, and who do not have access to other effective treatment options.

Subjects will be eligible to receive study drug (BCX9930) under this version of the protocol for up to 96 weeks for as long as the investigator believes it is in the subject’s best interest to continue treatment, or until the subject has access to another therapy for PNH, whichever comes first. Treatment with BCX9930 will be discontinued for subjects who are deriving no meaningful clinical benefit, or who experience an unacceptable drug-related AE or are otherwise intolerant of study drug.

An independent BCX9930 program-wide DMC will provide oversight of the safety of subjects receiving BCX9930 in this study.

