### 5.4. Analysis Populations

#### 5.4.1. Safety Population

The safety population is defined as all subjects who receive at least 1 dose of study drug. This population will be used for all analyses of exposure, demographics, and safety.

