### **6.4. Exposure to Study Treatment**

The exposure to study treatment table for the subjects in the safety population will descriptively summarize the BCX9930 400 mg BID, dose taper and Total with the number and percentage of subjects dosed and descriptive statistics (i.e., mean, standard deviation, etc.) for the number of days of exposure.

The compliance data as reported on the eCRF will be listed.

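### The dose-taper column of the TEAE tables is divided by the whole safety population, including subjects who never tapered, and no exposure-adjusted rate accompanies the crude percentages.

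*SAP*

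**What the plan says.** SAP 8.1 sets the columns of the overall TEAE table (14.3.1.1): "Results will be summarized for the BCX9930 400 mg BID, dose taper and Total". The subject-level rule names no column: "The percentages for number of subjects will use the safety population sample size as the denominator". SAP 8.2.1, 8.2.2.1 and 8.2.2.2 repeat both the columns and the denominator for the SOC/PT, serious and non-serious tables (14.3.2.1, 14.3.2.3.1, 14.3.2.3.2). The renal and hepatic tables (SAP 8.2.2.3 and 8.2.2.4) use the same denominator but state no phase columns.

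SAP 5.4.1 fixes the population: "The safety population is defined as all subjects who receive at least 1 dose of study drug". Protocol 9.4.2 leaves both the decision to taper and the length of any taper to the investigator; the suggested schedule is blacked out in the public text.

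Treatment time varies by design. SAP 3.1 allows treatment for "up to 96 weeks for as long as the investigator believes it is in the subject’s best interest to continue treatment", or, as the Technical Summary Report also says, "until the subject has access to another therapy for PNH, whichever comes first".

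The plan is not limited to percentages of subjects. SAP 8.1 adds event counts ("the table will also summarize the total number and percentage for each of these events"), although "the percentages for the number of events will use the total number of TEAEs as the denominator". SAP 6.4 gives the number dosed and "descriptive statistics (i.e., mean, standard deviation, etc.) for the number of days of exposure" for 400 mg BID, dose taper and Total. Neither the SAP nor protocol 13.3.4 defines person-time, an exposure-adjusted incidence or a time-to-first-event display.

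**The concern.** A subject who never enters the taper phase cannot have a taper-period event. Counting that subject in the denominator lowers the taper percentage by a factor that depends only on how many subjects tapered. A reader who compares the taper and 400 mg BID columns would be comparing figures with different at-risk groups under a common N.

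The second issue is time at risk. The study is titled and framed as long-term safety, and subjects may leave at any point up to 96 weeks for reasons such as access to another therapy. A percentage of subjects with an event then cannot be read, or set beside another study, without knowing how long those subjects were followed.

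**Working it through.** The documents give no AE rate, exposure distribution or taper frequency, and the N of up to 30 does not come from a calculation (SAP 3.3). There is no planned figure to reproduce. What follows is illustration under stated assumptions.

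**1. Denominator of the taper column (no rate assumption needed)**

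Inputs: N = 30 (SAP 3.3, maximum). Assumed: k subjects taper and 3 of them have a taper-period TEAE.

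Printed = 3/30 = 10%. Among those at risk = 3/k. Understatement factor = 30/k.

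| Subjects tapering (k) | Printed | Among those who tapered | Factor |
|---|---|---|---|
| 5 | 10% | 60% | 6 |
| 10 | 10% | 30% | 3 |
| 15 | 10% | 20% | 2 |
| 30 | 10% | 10% | 1 |

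The error disappears only if everyone tapers.

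**2. Crude percentage and time on drug**

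Assumed: constant first-event rate r per person-year. Crude incidence = 1 − exp(−r × days/365.25).

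| Time on drug | r = 0.1 | r = 0.5 | r = 2 |
|---|---|---|---|
| 24 weeks | 4.5% | 20.5% | 60.1% |
| 48 weeks | 8.8% | 36.9% | 84.1% |
| 96 weeks | 16.8% | 60.1% | 97.5% |

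Down a column, time changes the percentage; along a row, the rate changes it. Both matter.

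**3. One crude percentage, different rates**

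Assumed: 6 of 30 subjects have an event, which is 20% in each case. Person-years are total time on drug, not cut at first event and without the 30-day window.

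- All complete 96 weeks: 30 × 672/365.25 = 55.2; 6/55.2 = 10.9 per 100 person-years (exact Poisson 95% interval 4.0 to 23.7).
- Half stop at Week 48: (15 × 672 + 15 × 336)/365.25 = 41.4; 14.5 per 100.
- All stop at Week 24: 30 × 168/365.25 = 13.8; 43.5 per 100 (16.0 to 94.6).

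**4. What a rate can deliver in the taper column**

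Assumed: 10 subjects taper for 2 weeks. Person-time = 10 × 14/365.25 = 0.38 years. One event gives 261 per 100 person-years, exact 95% interval about 7 to 1,450. The denominator correction helps this column; a rate barely does.

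**5. Events after the last dose**

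SAP 5.6.4 counts AEs up to 30 days after last dose as TEAEs but assigns them to no column. Protocol 12.4 collects AEs only to the last study visit, which protocol 10.1 places about 3 weeks (± 3 days) after last dose, so the full 30 days will usually not be observed.

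**The case against.** Crude incidence is what was specified. Subject incidence is the endpoint (SAP 2.2), protocol 13.3.4 asks for proportions, the study has one arm and no tests, and the SAP supports an abbreviated report of a terminated programme. That stands: the crude percentages are legitimate and should stay, and the rate is an addition.

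The exposure context is also reported. Total events per person-year can be approximated from the event counts and the number dosed times mean days in SAP 6.4, and listings 16.2.5.1 and 16.2.7.1 give subject-level exposure and TEAEs. That stands too, but first-event rates would have to be rebuilt from the listings.

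A programmer might take the safety population sample size to mean the N of each column. That would remove the first problem, but the text does not say it, and the population definition points the other way.

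Three stronger readings are tempting:

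- A reader might infer that the percentages mainly reflect time on drug. The documents give no rate or exposure distribution from which to show this, and the table in step 2 shows that the rate matters as well.
- A reader might infer that exposure runs from a few days of taper to 96 weeks. Taper is a phase at the end of a subject's treatment, not that subject's whole exposure, and its length is not visible.
- A reader might infer that the taper column hides the period of greatest hemolysis risk. Protocol 12.5.3 ties severe hemolysis to permanent discontinuation, within days of stopping, and not specifically to the taper.

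**Conclusion.** The point holds in two parts. First, in Tables 14.3.1.1, 14.3.2.1, 14.3.2.3.1 and 14.3.2.3.2, the rule as written understates taper-period incidence by the factor N divided by the number who tapered: threefold if 10 of 30 taper. This needs no assumption about rates, only that not everyone tapers. Second, no exposure-adjusted rate is planned although time on drug may vary up to 96 weeks. A crude 20% could correspond to anything from 10.9 to 43.5 per 100 person-years across the exposure patterns assumed here. This limits interpretation; it is not an error in the endpoint. The phase-column argument does not extend to the renal and hepatic tables, which state no such columns. All AE rates, taper lengths, taper counts and dropout patterns used above are assumptions.

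**What to change.** 1. In Tables 14.3.1.1, 14.3.2.1, 14.3.2.3.1 and 14.3.2.3.2, use the number of subjects dosed in each phase, already produced under SAP 6.4, as that column's denominator, and print it in the column header.
2. Keep the crude percentages. Add subjects with an event per 100 person-years at risk, with exact Poisson 95% intervals, at least in Table 14.3.1.1 and for the Total in Tables 14.3.2.4 and 14.3.2.5. Time at risk runs to the first event or to the end of the TEAE window, or to the last study visit if that comes earlier.
3. State which column receives TEAEs in the 30 days after last dose, and count that time in the same column's person-time.

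Cost: item 1 is a change of denominator. Items 2 and 3 need first-event truncation and a window-assignment rule, but use dates already held. SAP 1 allows the plan to change before database lock; after that, the change can be noted in the study report. Downsides: the rate assumes a roughly constant hazard in subjects already treated for at least 12 weeks, so Day 1 here is not the start of exposure. With N up to 30 the intervals will be wide, and a taper rate may be too imprecise to use.

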### **8.2. Adverse Event Preferred Term and Body/Organ System Summary Tables**

#### **8.2.1. Treatment-emergent Adverse Events by System Organ Class and Preferred Term**

A summary of the number and percentage of subjects with treatment-emergent adverse events by system organ class and preferred term will be presented along with the number of events for all subjects in the safety population. Results will be summarized for the BCX9930 400 mg BID, dose taper and Total. The percentages for number of subjects will use the safety population sample size as the denominator.

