## **8.3. Subject Withdrawal**

Participation in the study is strictly voluntary; a subject may withdraw consent to contribute additional study information at any point. Subjects have the right to withdraw from the study at any time and for any reason. In addition, a subject's participation may be terminated for any of the reasons described in Section [7.4.1](#). Whenever possible, the investigator will consult with the sponsor medical monitor before halting a subject's participation in the study.

Although a subject may withdraw from the study at any time without specifying a reason for withdrawal, the reason for withdrawal, if provided by the subject, will be recorded in the subject's medical records (source documents) and also in the eCRF. If the reason for subject withdrawal is not known, attempts to contact the subject must be documented to establish whether the reason was due to an AE, and if so, this must be reported in accordance with the procedures outlined in Section [12.4.1](#). Vigorous attempts will be made for follow-up of all subjects who miss a study visit, given the potential for hemolysis if BCX9930 dosing is interrupted. If at any point in the study the clinic is unable to contact the subject after appropriate attempts have been made, the subject will be considered lost to follow-up. If a subject's participation in this study is terminated, the responsible investigator/clinical staff member will document termination in the source documents.

Unless consent is withdrawn, subjects who discontinue study treatment will be monitored for potential hemolysis and may be required to return to the clinic for an additional visit(s) to assess for acute symptomatic hemolysis, if and when symptoms occur. A dose tapering schedule should be considered (Section [9.4.2](#)). An early termination (ET) visit will be completed approximately 3 weeks after the date of last dose of BCX9930 (see [Table 2](#)).

Once subjects have withdrawn from the study, the sponsor will no longer provide treatment through the study.

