#### 9.4.2. Dose Tapering

In the event of permanent discontinuation of BCX9930, CCI

The decision to taper the dose and duration of any taper should be based on the investigator's medical judgement, taking into account the reason for discontinuation of the drug, the severity of any reported signs or symptoms, and/or any reported worsening of signs or symptoms. The tapering schedule should be discussed with the sponsor medical monitor (or designee), ideally prior to implementation, and adjusted, as appropriate, for the individual subject.

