**CCI**

**CCI**

#### **12.4.2. Pregnancy**

Any female subject who becomes pregnant during the course of the study should have BCX9930 discontinued immediately and must be followed through the end of the pregnancy. While pregnancy is not considered an AE, all cases of fetal drug exposure via the parent as a study participant (including partners of study participants) are to be reported immediately to BioCryst or its designee. Consent from study partners who become pregnant will be obtained prior to reporting any details of the pregnancy. Information related to the pregnancy must be given on a “Pregnancy Notification and Outcome” form that will be provided by the sponsor or its designee so that the pregnancy may be followed, and an outcome determined. Any AEs or SAEs experienced by a pregnant subject are to be reported as directed in Section 12.4.1.

Any complications reported in a subject’s pregnant partner should be reported on the Pregnancy Notification and Outcome form. All pregnancies must be followed to outcome, which occurs when an infant is delivered (live or still born), there is fetal demise, or there is an abortion (spontaneous or induced). Abortion (spontaneous or induced), fetal demise, and still birth, along with congenital abnormalities in the newborn, should be reported as separate SAEs.

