## **6. STUDY POPULATION**

### **6.1. Subject Disposition**

The subject disposition table for all subjects will summarize the number and percentage of subjects that received at least one dose of study drug, discontinued treatment, the reasons for discontinuation, and subjects that completed the study. Results will be summarized for the BCX9930 treatment group.

The percentages for subjects dosed, discontinued, and completed will be based on the number of subjects enrolled. Percentages for discontinuation reason will be based on the number of subjects that discontinued.

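### Four SAP adverse-event tables divide the dose-taper column by the whole safety population, so it does not show incidence among subjects who tapered, and no rule says which events the column takes

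*SAP*

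**What the plan says.** SAP 8.1 sets out the columns of the overall TEAE table: "Results will be summarized for the BCX9930 400 mg BID, dose taper and Total". SAP 8.2.1 (all TEAEs by system organ class and preferred term), 8.2.2.1 (serious) and 8.2.2.2 (non-serious) use the same three columns. All four sections give the same rule for subject percentages: "The percentages for number of subjects will use the safety population sample size as the denominator". SAP 5.4.1 defines that population once, with no taper subset: "The safety population is defined as all subjects who receive at least 1 dose of study drug". The renal and hepatic tables (SAP 8.2.2.3 and 8.2.2.4) use the same denominator but specify no taper column, so four tables are affected.

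The protocol does not require a taper. Section 8.3 says "A dose tapering schedule should be considered". Section 9.4.2 says "The decision to taper the dose and duration of any taper should be based on" the investigator's judgement. Some stops are foreseen as immediate: a subject who becomes pregnant "should have BCX9930 discontinued immediately" (Protocol 12.4.2), and Protocol 12.5.1 allows an immediate stop for a hepatic event when medically indicated.

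The number who taper will be known. The exposure table in SAP 6.4 covers "BCX9930 400 mg BID, dose taper and Total with the number and percentage of subjects dosed".

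On timing, SAP 5.6.4 counts events up to 30 days after the last dose as treatment-emergent and puts taper-period events in the tables. Protocol 9.4.1 allows dose reduction and interruption. No sentence says which column takes events that start after the last dose, on a reduced dose or during an interruption.

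**The concern.** A subject who never enters a taper cannot have an event during one, yet is counted in the taper column's denominator. The column stands beside 400 mg BID under a phase label, and nothing in the four sections warns against reading it as the incidence in that phase. Read that way, it is too low whenever fewer subjects taper than were treated. Stopping is a period of clinical interest, because Protocol 12.5.3 describes a risk of severe hemolysis on permanent discontinuation.

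The missing allocation rule is part of the same problem. Until the plan says which events enter the taper column, its numerator is not fixed, and no choice of denominator gives the percentage a clear meaning.

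**Working it through.** The plan has no figure to reproduce: there is no sample size calculation and no hypothesis test. The check is algebra with assumed values.

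**Inputs**
- N, subjects in the safety population: 30, the planned maximum (SAP 3.3).
- k, subjects who enter a taper: not in the documents. Varied from 10 to 30 as an assumption.
- x, subjects with an event counted in the taper column: 1 or 3, for illustration.

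**Formulas**, if the column counts only events that start during a taper in subjects who tapered:
- printed percentage = x/N
- incidence among those who tapered = x/k
- ratio = (x/k)/(x/N) = N/k, whatever x is
- largest percentage the column can print = k/N, reached when every tapering subject has an event

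**Results for N = 30.** The table prints 1/30 = 3.3% for one subject and 3/30 = 10.0% for three, whatever k is.

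| k | Cap k/N | Factor N/k | x=1: x/k | Gap from 3.3%, points | x=3: x/k |
|---|---|---|---|---|---|
| 30 | 100% | 1.0 | 3.3% | 0 | 10.0% |
| 28 | 93.3% | 1.07 | 3.6% | 0.2 | 10.7% |
| 25 | 83.3% | 1.2 | 4.0% | 0.7 | 12.0% |
| 20 | 66.7% | 1.5 | 5.0% | 1.7 | 15.0% |
| 15 | 50.0% | 2.0 | 6.7% | 3.3 | 20.0% |
| 10 | 33.3% | 3.0 | 10.0% | 6.7 | 30.0% |

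**Why the condition matters.** Suppose events after the last dose also go into the taper column, and k = 10. If 2 tapering and 2 non-tapering subjects have events, the table prints 4/30 = 13.3%. Incidence among those who tapered is 2/10 = 20.0%. The ratio is 20.0/13.3 = 1.5, not 30/10 = 3.0, and 4/10 would not be a proportion of the tapering subjects at all. The factor N/k therefore depends on an allocation rule that the SAP does not state.

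**What is unaffected.** Total uses N, which is right for that column. Event percentages in SAP 8.1 use the total number of TEAEs, so N/k does not apply to them. The 400 mg BID column changes little if nearly all subjects receive that dose.

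**The case against.** The strongest reply is that x/N is a valid and openly stated quantity: the share of all treated subjects who had an event during a taper. One denominator also keeps the columns on a common base, and the SAP nowhere says that the taper column estimates incidence among those who tapered. This stands. The column is not miscalculated; the difficulty is how a phase column is likely to be read when no n is shown.

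The second reply is that the effect may be nil. Treatment is capped at 96 weeks and development has ended, so every subject is expected to stop, and stopping is what prompts a taper. Part of Protocol 9.4.2 is redacted, so how strongly tapering is advised cannot be seen. This also stands: nothing makes k=10 more likely than k=28.

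Third, readers can recompute the figure from the counts and the SAP 6.4 table. They can, but only by going to another table.

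Fourth, the phases differ in length, so changing the denominator does not make the columns comparable per unit of time. This is correct and limits what the change achieves.

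The SAP's own handling of subsets offers only loose support for the change. Under SAP 6.1, "Percentages for discontinuation reason will be based on the number of subjects that discontinued", but that is a breakdown within one group of subjects, and other percentages in the same section use all enrolled subjects. It sets no convention for column denominators.

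**Conclusion.** The point holds as a minor descriptive one. As written, the four tables put subjects who never tapered into the taper column's denominator, and the column cannot exceed k/N if only tapering subjects contribute to it. On that same condition it is lower than the incidence among tapering subjects by N/k: between 1.0 and 3.0 for k from 30 to 10 with N = 30, and at most 1.2 if 25 or more taper.

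A reader might infer that the taper percentages are understated by N/k in every case, or by a large amount. The documents support neither. The exact factor needs the missing allocation rule, and the size needs k, which is not given. Nor does the plan hide taper-period events: they are counted in the tables, they enter Total, and they are listed by subject. Total and the protocol endpoint do not change, and no test or stated decision rests on a taper percentage.

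**What to change.** Make both changes together in SAP 8.1, 8.2.1, 8.2.2.1 and 8.2.2.2.

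1. **Denominator.** For each phase column, use the safety-population subjects who received at least one dose in that phase, taking n from the SAP 6.4 exposure table. Print that n in the column header. Keep the full safety population for Total.
2. **Allocation.** State which column takes TEAEs that start after the last dose (within 30 days), or in reduced-dose or interrupted time. Keep TEAEs of subjects who never tapered out of the taper column, so that its numerator is a subset of its denominator. Use the same definition of the taper phase in the exposure table. A separate post-treatment column or flag is optional.

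The cost is one denominator sentence in each of four sections, new headers in four tables and one allocation sentence. No new data are needed. The latitude in SAP 9.1 covers titles, numbering, extra listings and split displays, not denominators, so the change belongs in a SAP revision before database lock or, after that, in the study report as a deviation.

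The downside is unstable taper percentages when few subjects taper. One subject with an event has an exact 95% interval of 0.1% to 24.9% at k=20 and 0.3% to 44.5% at k=10. Printing n makes this visible. The change does not adjust for different time at risk in the two phases.
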